STUDY PROTOCOL AND STATİSTİCAL ANALYSIS PLAN

TİTLE: The Effect of Rubber Dam on Objective and Subjective Parameters of Stress During Dental Treatment in Children

DOCUMENT DATE: 14.11.2024

RCT: The study was approved by the Medical Ethics Committee of Izmir Katip Celebi University, under report No. 2024/0242

STUDY PROTOCOL:

This randomized, controlled, single-blinded study included 100 healthy, cooperative children (Frankl Scale, Rating 3-4) aged 6-12 years, classified as ASA I, with bilateral fully erupted mandibular first permanent molars requiring pit and fissure sealant procedures. The inclusion criteria were based on the International Caries Detection and Assessment System II, including deep and retentive pits and fissures, no restorations, and no evidence of carious lesions.

The study was planned as split mouth design: For each patient, one tooth was selected for rubber dam isolation, while the corresponding tooth from the opposite quadrant was chosen for cotton roll isolation. The Rubber dam application group divided also into two groups as topical EMLA application, and infiltration anesthesia application. Randomization was performed using manually generated sealed envelopes containing information about which isolation method and anesthesia technique would be used on which side of the jaw (right or left). Random numbers were written on separate papers, folded, and placed in opaque sealed envelopes. Each participant chose an envelope and was assigned the printed participant number. Each number identified the teeth included in the study, the isolation technique specified for each tooth, and the anesthesia method to be used during the rubber dam application.

After the cleaning procedure, following the randomization result and determination of which isolation method would be applied to which side of the patient's jaw, to ensure that the local anesthetics used would not affect the patient's cooperation, in the first session, the selected tooth was isolated with standard cotton rolls and high-volume suction for the pit and fissure sealing procedure on one side of the patient. Cotton rolls were placed in both the lingual and mucobuccal side of the arch and the suction was positioned on the lingual side of the tooth. Cotton rolls were changed following enamel etching and, in every case, where they became excessively moisture throughout the treatment. The fissure sealant procedure was carried out following the manufacturer's instructions. Objective stress parameters (pulse rate, systolic blood pressure and diastolic blood pressure) for the children and the pulse rate of the operator were recorded at three different points. Systolic and diastolic blood pressure were measured using an automatic blood pressure monitor. Pulse rate was evaluated with a fingertip pulse oximeter. The operator's pulse rate was also recorded. Pain perception was assessed subjectively post-procedure using the Wong-Baker FACES Pain Rating Scale (WBFPRS) and Visual Analogue Scale (VAS). One week later, the patient was invited to a second appointment for the treatment of the corresponding tooth from the opposite side.

STATİSTİCAL ANALYSIS PLAN

All statistical analyses of the data were conducted using SPSS statistical software Version 21.0 (SPSS Inc., Chicago, IL, USA), with 0.05 selected as the level of significance (α). The normality test was conducted using Shapiro-Wilk and the Kolmogorov-Smirnov tests. Data were analyzed using Mann-Whitney U and independent samples t-tests. For within-group comparisons, Wilcoxon Signed Rank and the Friedman tests were employed.

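### The EMLA-versus-infiltration comparison uses valid unadjusted tests that forgo a modest precision gain from age, and possibly from screening Frankl rating

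*Combined protocol and SAP*

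**What the plan says.** The Study Protocol section sets eligibility: "This randomized, controlled, single-blinded study included 100 healthy, cooperative children (Frankl Scale, Rating 3-4) aged 6-12 years". The isolation contrast is within the child: "one tooth was selected for rubber dam isolation, while the corresponding tooth from the opposite quadrant was chosen for cotton roll isolation". The anaesthesia contrast is a subdivision of the rubber-dam side: "The Rubber dam application group divided also into two groups as topical EMLA application, and infiltration anesthesia application". Each child therefore receives only one of the two anaesthesia methods.

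On allocation, the same section says: "Each participant chose an envelope and was assigned the printed participant number". The number drawn fixes the teeth, the isolation method for each and the anaesthesia method. No strata, blocks or minimisation are described, by age, Frankl rating or anything else.

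On outcomes, it says: "Objective stress parameters (pulse rate, systolic blood pressure and diastolic blood pressure) for the children and the pulse rate of the operator were recorded". There are three such readings. The two pain scales are completed after the procedure only.

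The Statistical Analysis Plan says: "Data were analyzed using Mann-Whitney U and independent samples t-tests". It adds Wilcoxon signed-rank and Friedman tests within groups. It names no covariate, regression model or change score, and it gives no sample-size calculation, arm sizes or standard deviations.

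**The concern.** In the split-mouth contrast, each child is their own control, and stable traits such as age cancel when the analysis is paired. The EMLA-versus-infiltration contrast has no such protection. Any part of the outcome that varies with age, over an eligible span of 6 to 12 years, stays in the error term of a two-sample test.

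Age has to be established to admit a child, and so does a Frankl rating of 3 or 4. Neither can be altered by the envelope, which makes them clean covariates. Readings from the cotton-roll session are less clean, because that session follows the draw. The pain scales have no pre-procedure value of their own to adjust for.

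At stake is the width of the confidence interval for one between-child comparison. With every child contributing to only one arm, that comparison has less information than the paired one, so unused precision matters more there.

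**Working it through.** The plan has no figure of its own to reproduce, so this is an illustration for pulse only.

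**From the documents:** 100 children; ages 6 to 12 years; significance level 0.05.

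**Assumed:** 50 children per arm; total pulse SD 12 bpm; age SD 1.5 to 2.0 years; pulse changing by 1 to 3 bpm per year of age. The upper age SD is that of ages spread evenly over the integers 6 to 12: sqrt((49 − 1)/12) = 2.0. The lower value allows for ages being more concentrated, as they may be when fully erupted, unrestored, caries-free first molars are required.

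**Unadjusted standard error of the arm difference:** 12 × sqrt(2/50) = 2.4 bpm, a 95% half-width of 1.96 × 2.4 = 4.70 bpm.

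**Share of pulse variance explained by age:** R² = (slope × age SD)² / 12². **Standard-error ratio after adjustment:** sqrt(1 − R²). **Equivalent unadjusted total:** 100 / (1 − R²).

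| Slope (bpm/year) | Age SD (years) | R² | SE ratio | SE narrowed by | Equivalent total |
|---|---|---|---|---|---|
| 1 | 1.5 | 2.25/144 = 0.016 | 0.992 | 0.8% | 102 |
| 1 | 2.0 | 4/144 = 0.028 | 0.986 | 1.4% | 103 |
| 2 | 1.5 | 9/144 = 0.063 | 0.968 | 3.2% | 107 |
| 2 | 2.0 | 16/144 = 0.111 | 0.943 | 5.7% | 113 |
| 3 | 1.5 | 20.25/144 = 0.141 | 0.927 | 7.3% | 116 |
| 3 | 2.0 | 36/144 = 0.250 | 0.866 | 13.4% | 133 |

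The formula ignores the small cost of estimating the covariate coefficients. In the first row or two, the net gain is therefore close to nil.

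**Chance age imbalance.** The standard error of the difference in mean age is 1.5 × 0.2 = 0.30 or 2.0 × 0.2 = 0.40 years. The probability of a gap of at least 0.5 years is about 10% to 21%, and of at least 1 year about 0.1% to 1.2%.

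**Imbalance and lost precision are the same quantity.** With age SD 2.0, a 95% age gap of 1.96 × 0.40 = 0.78 years moves the pulse difference by 1.57 bpm at 2 bpm per year, or 2.35 bpm at 3 bpm per year. Dividing by the 4.70 half-width and squaring gives (1.57/4.70)² = 0.11 and (2.35/4.70)² = 0.25. These are the R² values in the table, so the possible shift is already inside the unadjusted interval.

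**The case against.** The strongest case against is that this is a general preference for covariate adjustment, applied to a secondary subdivision of a very short plan. Much of that stands. The title question is rubber dam versus cotton roll, which is within the child. The unadjusted tests are valid under randomization, and at an assumed 50 per arm large age gaps are unlikely. The size rests on a slope, SDs and arm sizes that the documents do not give, and under the weaker assumptions the gain is negligible.

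It also stands that the plan does not say whether between-group tests use values or changes. If one of the three readings precedes the procedure and changes were analysed, age would add less for pulse and blood pressure. Frankl rating is already restricted to two cooperative levels, so age is probably the larger contributor.

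Three stronger readings are tempting, and the documents do not support them:

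- A reader might infer that the lack of stratification biases the anaesthesia comparison, or that imbalance is a second harm on top of lost precision. Random allocation rules out the first, and the arithmetic above rules out the second.
- A reader might infer that Frankl rating matters because it measures what the trial studies. The listed outcomes are pulse, blood pressure, operator pulse and two pain scales; there is no behaviour outcome.
- A reader might ask for stratified envelopes. The text reports the 100 children as already included, so that is probably moot.

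What the objection does not remove is that the covariates had to be ascertained anyway and that the listed tests cannot use them.

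**Conclusion.** The point holds as one of efficiency, confined to EMLA versus infiltration. The planned tests are valid but leave out baseline information that eligibility required. Under the stated assumptions, adjusting for age narrows the standard error of the pulse difference by about 1% to 13%, with age explaining about 2% to 25% of pulse variance. The upper end needs both an even age spread and a steep slope.

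Nothing is quantified for blood pressure, the pain scales or Frankl rating, and no claim about their size is made. That no adjustment was intended is read from the plan's silence. The paired rubber dam versus cotton roll contrast is unaffected. The change is worth making because it costs almost nothing, not because the unadjusted result would be wrong.

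**What to change.** For EMLA versus infiltration, specify the following in the Statistical Analysis Plan:

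- **Pulse, systolic and diastolic pressure:** a linear model at each recorded point of the rubber-dam session, with anaesthesia arm, age in years as a continuous term and, where the individual rating was kept, screening Frankl rating (3 or 4). Report the adjusted difference with its 95% confidence interval.
- **WBFPRS and VAS:** an ordinal (proportional-odds) model with the same terms.
- **Timing:** if the data have already been seen, report these as a sensitivity analysis alongside the unadjusted tests, and say so.

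The cost is a few lines of text and two degrees of freedom: with 100 children, the residual degrees of freedom of the linear model fall from 98 to 96. Age and Frankl rating had to be ascertained for eligibility, so no new measurement is needed. The plan gives only an eligibility range for Frankl, so if the individual ratings were not retained, age alone can be used at the cost of one degree of freedom.

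### Jaw side is randomised but the SAP assigns no test to it, so a right-left difference would cost the split-mouth comparison some precision

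*Combined protocol and SAP*

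**What the plan says.** The Study Protocol section states that "The study was planned as split mouth design", in 100 children, with one mandibular first molar under rubber dam and the opposite one under cotton rolls. On allocation it says that "Randomization was performed using manually generated sealed envelopes", and that these envelopes held "which isolation method and anesthesia technique would be used on which side of the jaw (right or left". It states no blocking, allocation ratio or right/left balance.

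The SAP section gives the level of significance and then the tests: "Data were analyzed using Mann-Whitney U and independent samples t-tests" and "For within-group comparisons, Wilcoxon Signed Rank and the Friedman tests were employed". It names no grouping variable, covariate, stratum or model. Side does not appear in it.

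**The concern.** Randomising side creates two groups of children, dam-right and dam-left, and the envelope records which group each child is in. The two teeth of a child are always on opposite sides. Pairing by child therefore removes the child's own level but leaves any right-left difference in place. If one side gives systematically higher readings (for example because it is harder for the operator to reach), the within-child difference is shifted one way in dam-right children and the other way in dam-left children. An analysis that does not know the side counts that spread as random error. What is at stake is some power for the children's pulse, blood pressure and pain scores, lost to a source of variation that the design has already identified.

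**Working it through.** **Inputs.** From the documents: 100 children, split-mouth, side randomised by envelope, α = 0.05. Assumed, because the documents are silent: a two-sided test, roughly normal differences, a paired dam-versus-cotton analysis, and s between 0.2 and 0.5 of the SD of the within-child difference. The plan states no power, effect size or SD, so there is no figure of its own to reproduce.

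**Model.** Let τ be the dam-minus-cotton effect, s the right-minus-left difference in a reading, and σ the SD of the within-child difference D without any side effect.

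- Dam-right child: D = τ + s + error.
- Dam-left child: D = τ − s + error.
- Sides 1:1 and side left out: Var(D) = σ² + s², an inflation of 1 + (s/σ)².

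**Variance and effective number.** The effective number of children is 100 / (1 + (s/σ)²).

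| s/σ | Inflation | Effective n |
|---|---|---|
| 0.2 | 1 + 0.04 = 1.04 | 96 |
| 0.3 | 1 + 0.09 = 1.09 | 92 |
| 0.5 | 1 + 0.25 = 1.25 | 80 |

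**Power.** Take the effect that 100 pairs detect with 80% power when s = 0: (1.96 + 0.84)/√100 = 0.28σ. Write f = √(1 + (s/σ)²) and Φ for the normal distribution function.

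- Simple randomisation of side: the estimate itself varies with the chance split, so power = Φ(2.80/f − 1.96).
- Exact 50/50 split: the side shifts cancel in the mean and only the estimated standard error is too large, so power = Φ(2.80 − 1.96f).

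| s/σ | f | Simple | Exact split |
|---|---|---|---|
| 0.2 | 1.020 | 78.4% | 78.9% |
| 0.3 | 1.044 | 76.5% | 77.5% |
| 0.5 | 1.118 | 70.7% | 72.9% |

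**Simulation** (40,000 runs per setting, n = 100, σ = 10, τ = 2.8), power without and with a side term:

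| s | Exact split | Simple randomisation |
|---|---|---|
| 0 | 79.6 / 79.6% | 79.1 / 78.6% |
| 2 | 78.1 / 79.3% | 77.8 / 79.0% |
| 3 | 76.5 / 79.1% | 75.7 / 78.8% |
| 5 | 71.8 / 79.0% | 70.4 / 79.1% |

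The loss is about 1, 3 and 7 points with an exact split, and about 1, 3 and 9 with simple randomisation. If there is no side effect, the side term costs at most about half a point.

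**Validity.** The simulated type I error of the unadjusted paired test was 0.050 to 0.051 under simple randomisation for s/σ from 0.2 to 1.0. Under an exact split it was 0.044 at s/σ = 0.2 and 0.029 at 0.5. Leaving side out does not raise false positives.

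**The listed tests can carry side.** The right-minus-left difference averages s + τ in dam-right children and s − τ in dam-left children. Comparing the two groups gives (s + τ) − (s − τ) = 2τ, from which s has dropped out. The independent t-test on these differences is the same analysis as the linear model with side, and half the difference in means estimates τ.

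**EMLA versus infiltration.** Assume 50 children per group and unrestricted allocation. The SD of the difference in dam-right share is √(2 × 0.25/50) = 0.10. With s = 2 to 5 bpm this moves the estimate by 0.2 to 0.5 bpm. The standard error, if single readings have SD 10, is 10 × √(2/50) = 2 bpm.

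**The case against.** The strongest reply is that this is optional refinement on assumed numbers. The documents report no right-left difference and do not say that access differs by side. A loss above 3 points needs a side effect larger than the treatment effect used in the calculation. If the SAP's independent-samples tests were applied directly to dam and cotton readings, side would make up only about 0.6% to 8% of the variance of the comparison (s of 0.2 to 0.5 SD, within-child correlation 0.3 to 0.7). All of this stands, and it limits the weight of the point.

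Two stronger readings are tempting and are not supported. A reader might infer that none of the listed tests could take side into account. Mann-Whitney U and the independent t-test both compare two groups and would adjust for side if applied to right-minus-left differences by allocation. The gap is that the SAP does not say so and leaves their grouping variable unnamed. A reader might also infer that any analysis stratified by side would help. A signed-rank test stratified by side does not, because it still measures each difference from zero. With σ = 10, τ = 2.8 and an exact split (20,000 runs), its power was 74%, 70% and 57% at s = 2, 3 and 5, against 76%, 74% and 69% for the plain signed-rank test. Mann-Whitney U on right-minus-left differences kept about 77% throughout.

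**Conclusion.** The point holds as a minor one. Side is randomised, the SAP assigns no test to it, and in a paired analysis any right-left difference goes into the error term. The cost is small up to about 0.3 SD and becomes noticeable only near half an SD. These sizes rest on assumed values of s and on a paired dam-versus-cotton analysis that the SAP does not explicitly specify.

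A reader might infer that leaving side out biases the dam-versus-cotton result. It does not: random allocation of side protects against systematic side bias, and the unadjusted paired test is valid or conservative in that respect. That reassurance covers side only. The Study Protocol section says that "in the first session, the selected tooth was isolated with standard cotton rolls", with the opposite tooth treated one week later, so isolation method is confounded with visit order. Adjusting for side does nothing about that. For EMLA versus infiltration, the effect of a chance side imbalance is small beside the standard error.

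**What to change.** Add one sentence to the SAP: the rubber dam versus cotton roll comparison uses the within-child dam-minus-cotton difference in a linear model with randomised side (dam right or dam left) as a factor, coded +1/−1 so that the intercept is the effect averaged over sides. An equivalent statement is that right-minus-left differences are compared between dam-right and dam-left children, with the independent t-test for pulse and blood pressure and Mann-Whitney U for pain scores. Do not use a side-stratified signed-rank test.

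Report the right/left split. If allocation was unrestricted, 95% of splits of 100 lie between 40/60 and 60/40. A side term in the EMLA versus infiltration comparison is optional. If results had already been seen when the sentence is added, label the side-adjusted analysis as supplementary.

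The cost is one sentence and one degree of freedom out of about 100. Side is already fixed by each envelope, so no new data are needed and nothing in the children's care changes.

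### One envelope fixes the anaesthesia method before the cotton-roll session, a week before it is needed, with no later unsealing or masking described, so knowledge of the arm can affect session-1 readings and return for session 2

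*Combined protocol and SAP*

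**What the plan says.** The Study Protocol's paragraph on the split-mouth design describes "sealed envelopes containing information about which isolation method and anesthesia technique would be used on which side of the jaw (right or left"). The child draws it: "Each participant chose an envelope and was assigned the printed participant number". On what that number settles, the protocol says: "Each number identified the teeth included in the study, the isolation technique specified for each tooth, and the anesthesia method to be used" for the rubber dam tooth.

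The next paragraph of the Study Protocol gives the timing. Treatment starts "following the randomization result and determination of which isolation method would be applied to which side of the patient's jaw", and the order is the same for everyone: "in the first session, the selected tooth was isolated with standard cotton rolls and high-volume suction". The reason given for this order is "to ensure that the local anesthetics used would not affect" cooperation. The dam tooth is treated later: "One week later, the patient was invited to a second appointment".

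The outcomes are the child's pulse and blood pressure, the operator's pulse, and the child's pain ratings after the procedure. The study is called single-blinded, but the blinded party is not named. The documents do not say who opens the envelope, who reads it or who is told its content. They describe no later opening of the anaesthesia assignment and give no rule for a child who misses the second session.

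**The concern.** Session 1 needs one piece of the allocation: which side gets cotton rolls. The anaesthesia method is not used until the dam session. Carrying both in one envelope makes the second available a week early to anyone who reads the first.

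This matters because the outcomes respond to expectation. A child who expects an injection next week, or an operator who expects to give one, may have a higher pulse in session 1 than under EMLA. Such a shift would enter the cotton-roll readings, which are one side of the dam-cotton contrast. It would make the dam look better relative to cotton rolls: a true excess of stress under the dam would shrink, and a true reduction would be exaggerated.

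The second route is attendance. EMLA and infiltration are compared only in session 2. If families learn the arm after session 1 or before it, the decision to return can depend on it, and the groups compared in session 2 are then no longer the groups that were randomised.

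**Working it through.** The plan states no figure on this point, so there is none to reproduce. It gives 100 children and a significance level of 0.05, but no SD, effect size, non-return rate or EMLA:infiltration ratio.

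**Order of steps, from the Study Protocol**
1. The child draws one envelope; its number settles side, isolation and anaesthesia.
2. The side is determined from the randomisation result.
3. Session 1: cotton rolls, for every child.
4. One week passes.
5. Session 2: rubber dam, with EMLA or infiltration.

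The anaesthesia assignment exists from step 1 and is first needed at step 5. Nothing described keeps it from whoever performs step 2.

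**Assumptions for the sizes (not in the documents)**
- 50:50 split, outcomes in SD units, two-sided 0.05, normal approximation.
- Anticipation shift a = 0.2-0.4 SD in the infiltration half only.
- Within-child correlation between sessions ρ = 0.3-0.7.
- Non-return f = 5-20% of infiltration children, who lie d = 0.5-1.0 SD above their group average.

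**Route 1: anticipation and the dam-cotton contrast**

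Bias in the cotton-roll mean = a/2: 0.2/2 = 0.1 SD to 0.4/2 = 0.2 SD.

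For a within-child contrast in 100 children, SE = √(2(1−ρ)/100). The table gives the chance of a significant result when there is no true difference (nominal 5%).

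| ρ | SE (SD) | 95% half-width, 1.96 × SE | a = 0.2 | a = 0.3 | a = 0.4 |
|---|---|---|---|---|---|
| 0.3 | 0.118 | 0.23 | 13.5% | 24.5% | 39% |
| 0.5 | 0.100 | 0.20 | 17% | 32% | 52% |
| 0.7 | 0.077 | 0.15 | 25% | 49% | 73% |

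Example: with ρ = 0.5 and a = 0.2, z = 0.1/0.100 = 1.0, and Φ(1.0 − 1.96) + Φ(−1.0 − 1.96) = 0.17. The SAP does not say which of its tests serves the dam-cotton contrast; the bias of a/2 is the same whichever is used, but the rejection rates are for a paired analysis.

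**Route 2: non-return and EMLA v infiltration**

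If a fraction f leaves and lies d above the whole group's average, the mean of those who return falls by f·d/(1−f).

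| f | d = 0.5 | d = 1.0 |
|---|---|---|
| 5% | 0.025/0.95 = 0.026 | 0.05/0.95 = 0.053 |
| 10% | 0.05/0.90 = 0.056 | 0.10/0.90 = 0.111 |
| 20% | 0.10/0.80 = 0.125 | 0.20/0.80 = 0.25 |

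The 95% half-width for 50 v 50 is t(98) × √(2/50) = 0.397 SD. With 20% lost from one arm, SE = √(1/50 + 1/40) = 0.212, and the worst case of 0.25 SD gives z = 1.18 and a rejection rate of about 22%. At f = 10% and d = 0.5 it is about 6%. Relative to the precision of its own comparison, route 2 is the smaller unless the loss is large.

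**The case against.** The strongest objection is that disclosure is inferred. The text does not say that the operator or the child was told the anaesthesia method in session 1. The sentence on timing refers only to the side and isolation method. The wording about assigned numbers could describe a code with a separate key, in which case the draw tells the child nothing, and the unnamed blinded party could be the child. This stands as a limit: one may say that the arm can be known, not that it was. It does not remove the point, because the protocol also says that the envelopes hold the anaesthesia information, someone must read the allocation to set the side, and no step withholds the rest.

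Several stronger readings are tempting, and the documents do not support them:
- **That the plan defeats its own reason for putting cotton rolls first.** That reason concerns anaesthetics actually used. Knowing an assignment early does not contradict it.
- **That the envelope is why a child lost after session 1 lacks only dam readings.** That follows from the fixed order and would be the same with two envelopes.
- **That session 1 is spoiled as a child's own baseline for EMLA v infiltration.** The SAP plans no such adjusted comparison, and an unadjusted session-2 comparison is not biased by session-1 anticipation.
- **That the anticipation bias should be judged against 0.40 SD.** That half-width belongs to two independent groups of 50, not to a within-child contrast.
- **That allocation concealment before enrolment is broken.** The issue is what can be known after allocation.

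It is also fair to say that every effect size here is assumed, and that no non-return is reported.

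**Conclusion.** The point holds as an avoidable weakness of the allocation procedure. It is not evidence that bias occurred. The documents establish that one envelope carries both assignments, that session 1 follows the randomisation result, that the anaesthesia method is first needed a week later, and that no unsealing or masking step is described.

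Under the stated assumptions, anticipation biases the cotton-roll mean by 0.1-0.2 SD. At a within-child correlation of 0.5 that is about half to all of the 0.20 SD half-width of a paired contrast. Selective non-return lowers the infiltration mean by 0.03-0.25 SD. Both are zero if nobody involved in session 1 knew the arm and no family learned it before session 2. The documents do not settle whether that was so.

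**What to change.** Split the allocation into two concealed steps under the same participant number. Envelope 1 gives only the side and isolation method. Envelope 2 gives EMLA or infiltration and stays sealed until the child attends session 2. State in the protocol who opens each envelope, and who is blinded.

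This prevents arm-specific anticipation in session 1 and arm-dependent non-return before session 2. It does not remove anticipation common to both arms: if families know that an injection is possible, that expectation may still be present in the cotton-roll readings and so in the pooled dam-cotton contrast.

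The protocol is written in the past tense, so enrolment may be complete. In that case, report who knew the anaesthesia arm and when, session-1 values by arm, and session-2 attendance by arm.

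This is a cheap improvement. Its cost is about 100 extra envelopes kept sealed for a week, with no extra visits, staff or patients.

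### Cotton rolls always come at the first visit and the rubber dam at the second, so the title comparison cannot be separated from a visit effect, and the plan does not say so

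*Combined protocol and SAP*

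**What the plan says.** The title presents the study as "The Effect of Rubber Dam on Objective and Subjective Parameters of Stress During Dental Treatment in Children", and the STUDY PROTOCOL opens with "This randomized, controlled, single-blinded study included 100 healthy, cooperative children". The design is split mouth: "one tooth was selected for rubber dam isolation, while the corresponding tooth from the opposite quadrant was chosen for cotton roll isolation".

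The randomisation text describes sealed envelopes "containing information about which isolation method and anesthesia technique would be used on which side of the jaw (right or left". A later sentence in the same paragraph lists what each number fixes: the teeth, the isolation technique for each tooth, and "the anesthesia method to be used during the rubber dam application". Neither description mentions visit order.

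The procedure text then sets the order: "in the first session, the selected tooth was isolated with standard cotton rolls and high-volume suction". The reason given is "to ensure that the local anesthetics used would not affect" the child's cooperation. After that, "One week later, the patient was invited to a second appointment for the treatment of the corresponding tooth from the opposite side".

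The STATISTICAL ANALYSIS PLAN names Mann-Whitney U and independent samples t-tests, with Wilcoxon signed rank and Friedman tests for within-group comparisons. It does not say which test compares dam with cotton rolls. Neither part of the document mentions a visit effect or any limit on how that comparison may be read.

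**The concern.** A child's first and second appointments can differ in pulse, blood pressure and reported pain for reasons unrelated to isolation. Familiarity could lower the second set of readings and anticipation could raise them; the documents do not indicate which. If every child has cotton rolls first and the dam second, such a difference passes straight into the dam-versus-cotton result. Randomising jaw side protects against left-right differences and does nothing about visit.

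At stake is the title question, on every outcome compared between dam and cotton: child pulse, blood pressure, operator pulse, the Wong-Baker scale and the VAS. A reader who sees a randomised label and a title about the effect of the dam would take the difference as randomised evidence on the dam, which the described design cannot supply.

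**Working it through.** The plan gives no power, effect size or SD, so there is no figure of its own to reproduce. The main check is structural and needs no assumed effect size.

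**Inputs from the STUDY PROTOCOL.** 100 children; one dam tooth and one cotton-roll tooth each; cotton rolls in session 1; the opposite tooth one week later; side and anaesthesia technique randomised. With two teeth, one method per tooth, and cotton rolls used first, the dam must be at visit 2. The stated reason for the order would apply to every child, so it is read as fixed for all.

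**Model.** Response = child intercept + δ·dam + π·visit 2 + σ·side + error. Taking visit 2 minus visit 1 removes the child intercepts. In that difference:

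- the dam column is +1 for every child;
- the visit column is +1 for every child;
- the side column is +1 or −1, according to the envelope.

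The expected difference is therefore δ + π ± σ. Rank after child intercepts:

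| Columns | Order as described | If order varied between children |
|---|---|---|
| dam, side | 2 of 2 | not needed |
| dam, visit | 1 of 2 | 2 of 2 |
| dam, visit, EMLA, infiltration | 2 of 4 | 3 of 4 |

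Side can be separated from the dam; visit cannot. In the last row, one of the two deficiencies comes from the fixed order. The other (dam = EMLA + infiltration) would exist under any order, because the document describes the dam only with one of the two anaesthetics. In full-matrix terms, 100 child columns plus dam and visit make 102 columns with rank 101. Adding side gives 103 columns with rank 102, so the deficit remains.

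**Illustration of size.** Assumptions not in the documents: no dam effect, normally distributed within-child differences, two-sided 0.05, and a visit effect of d SDs of the within-child difference. For a paired test, the normal approximation to the rejection probability is Φ(d√n − 1.96) + Φ(−d√n − 1.96). With n = 100, d√n is 1, 2 and 3 for d = 0.1, 0.2 and 0.3:

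- d = 0.1: Φ(−0.96) + Φ(−2.96) = 0.170
- d = 0.2: Φ(0.04) + Φ(−3.96) = 0.516
- d = 0.3: Φ(1.04) + Φ(−4.96) = 0.851

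Simulating the Wilcoxon signed rank test, which the SAP names, under the same assumptions (40,000 runs; 20,000 at n = 400):

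| n | d = 0 | d = 0.1 | d = 0.2 | d = 0.3 |
|---|---|---|---|---|
| 50 | 0.050 | 0.104 | 0.275 | 0.524 |
| 100 | 0.049 | 0.164 | 0.488 | 0.826 |
| 200 | 0.049 | 0.277 | 0.786 | 0.986 |
| 400 | 0.053 | 0.494 | 0.973 | 1.000 |

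Only n = 100 is the trial's size. The other rows show that more children make the false attribution more likely.

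**EMLA versus infiltration.** Both arms are observed at visit 2, so a visit shift common to both cancels. With a shared shift of 0.3 SD and 100 children in all, Mann-Whitney U rejected at 0.050, 0.050, 0.051 and 0.050 for splits of 50:50, 40:60, 30:70 and 20:80 (40,000 runs each; splits assumed, because no allocation ratio is given). This contrast is not affected.

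**The case against.** The order was a deliberate choice, disclosed with a reason, and varying it would have meant anaesthesia at the first visit for some children. Jaw side and anaesthesia technique were randomised, so the label is not false. The SAP states no estimand or conclusion; the causal reading comes from the title. All of that is fair. It means the fault is not concealment and the sequence need not change. But a reason for a fixed order does not remove the confounding, and nothing in the document tells the reader that the title contrast is limited by it.

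A second objection is that the listed tests might escape the problem. Friedman could be run across the three recording points within a session, where a constant visit shift cancels. That compares times within one condition and does not compare dam with cotton. Within-session change scores could be compared between conditions, but only if one of the three points precedes isolation and anaesthesia, which the document does not say. They would remove only a constant shift, and they cannot help the pain scales, which are collected after the procedure.

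Third, the percentages depend on the test. If Mann-Whitney U were applied to the same paired data, rejection at 0.2 SD would be 34%, 21% or 6% for assumed within-child correlations of 0.3, 0.5 or 0.7, and 9%, 4% or 1% at 0.1 SD. This stands: no single percentage is the trial's risk. The bias in the difference is the same under any test. The illustration also assumes independent differences, which need not hold for operator pulse, since the number of operators is not stated.

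**Conclusion.** The concern holds and must be fixed. As described, dam versus cotton is fully aliased with visit: the estimate is δ + π, and no test or covariate applied to that difference can separate the two. This rests only on the stated order and on the inference, firm though not explicit, that visit 2 is the dam visit. The direction and size of any visit effect are unknown. The rejection rates of 16%, 49% and 83% are conditional on assumed visit effects of 0.1, 0.2 and 0.3 SD and on the Wilcoxon signed rank test. For pulse and blood pressure a partial remedy may exist if a pre-isolation reading was taken; for the two pain scales none does. EMLA versus infiltration remains a valid randomised comparison with respect to a visit effect common to both arms. A secondary labelling point stands apart from visit order: the contrast is dam plus anaesthetic against cotton rolls, not the dam alone.

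**What to change.** 1. In the STUDY PROTOCOL, state that visit order was fixed, with the reason already given, and that only jaw side and anaesthesia technique were randomised.
2. In the STATISTICAL ANALYSIS PLAN, define and report the isolation contrast as visit 2 (dam plus anaesthetic) minus visit 1 (cotton rolls), and say that it cannot be attributed to the dam alone.
3. Reserve randomised causal wording for EMLA versus infiltration.
4. Optionally, if one of the three pulse and blood pressure recordings precedes isolation and anaesthesia, also analyse within-session change from it. State that this removes only a constant visit shift, may be noisier, and does not apply to the pain scales.

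Items 1 to 3 are wording changes that need no new data or recruitment and can be made even if treatment is complete. Item 4 uses recordings already taken. The cost is a narrower conclusion on the title question. No change to the clinical sequence is proposed.
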